#### 4.6.4. Trial Rationale

KRAS is mutated in one quarter of human solid tumors, including the vast majority of pancreatic cancers, and substantial portions of colorectal, non-small cell lung, ovarian, gallbladder and bile duct cancers. KRAS is a validated oncogene that when mutated drives tumor growth and maintenance. Enhancing the T-cell immune response to tumors by utilizing the targeted KRAS ELI-002 product candidate has the potential to improve the outcomes of subjects who have undergone resection surgery and/or who have MRD following locoregional therapy, a clinical setting with the highest ratio of ELI-002 induced T cells to target tumor cells. For example, the pancreatic population selected for this trial is comprised of subjects who have already received chemotherapy/ chemoradiation (in the neoadjuvant and/or adjuvant setting) as well as pancreatectomy with an R0 (no residual tumor cells observed) or R1 (microscopic residual tumor cells observed) outcome, yet who have poor prognosis with persistent ctDNA post-surgery indicating an expected median relapse-free survival (RFS) of only 5 months [[Groot et al, 2019](#)]. The selection of cancer patients with MRD for evaluation of a cancer immunotherapy product candidate has several potential advantages:

- Maximization of the effector T-cell:target tumor cell ratio by minimization of tumor burden by successful prior therapy
- Maximization of T-cell trafficking potential because the fibrous stromal present in advanced tumors that can exclude T-cells has not yet formed
- Clinical settings where cytotoxic chemotherapy is not utilized, preserving the full potential of induced T-cells to persist and traffic

The Phase 1 study is an open-label, single-arm, dose-escalation trial incorporating a 3+3 design in subjects with KRAS/NRAS mutated PDAC and other solid tumors who have MRD.

Approximately 18 subjects are planned to be enrolled in Phase 1 to evaluate the safety, tolerability, and exploratory pharmacodynamic efficacy of SC ELI-002 using the adjuvant at 3 planned dose levels (Amph-CpG-7909 0.1 mg SC, 0.5 mg SC, 2.5 mg SC) in combination with a fixed dose of Amph-Peptides (700 µg each). Additional cohorts may be added to explore intermediate or higher dose levels. This will be based on the cumulative safety review and preliminary review of efficacy. If additional cohorts are added, this will be documented in a study memo sent to all clinical sites and submitted to IRBs, per IRB guidance.

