## 10.5. Follow-up Period

A Follow-up Period will provide safety and efficacy data ([Table 15](#) and [Table 16](#)).

At every visit during the Follow-up Period, **Visit 16 (Day 231), Visit 17 (Day 259), Visit 18 (Day 315), Visit 19 (Day 399), Visit 20 (Day 483), Visit 21 (Day 567), Visit 22 (Day 651), Visit 23 (Day 735), Visit 24 (Day 819), Visit 25 (Day 903), Visit 26 (Day 987), Visit 27 (Day 1071) and Visit 28/End of Study (Day 1127)**, the following visit procedures will include:

- Confirm ECOG Scale of Performance Status.
- Collect a blood sample for ctDNA test (central laboratory).
- Record any AEs that occur within 30 days of last dose and follow any such AEs until they resolve or return to baseline level.

In addition, the following assessments will be conducted at these Follow-up visits:

At **Visit 16 (Day 231)**, the following visit procedures will include

- Collect a blood sample for clinical laboratory assessments, including the cytokine panel (local laboratory; see [Section 11.1](#) and [Section 12.1.6](#)).
- Collect a whole blood sample for immunogenicity testing (central laboratory).

At **Visit 16 (Day 231), Visit 17 (Day 259), Visit 18 (Day 315), Visit 19 (Day 399), Visit 20 (Day 483), Visit 21 (Day 567), Visit 22 (Day 651), Visit 23 (Day 735), and Visit 24 (Day 819)** the following visit procedures will include

- Administer the EORTC QLQ-C30 and the tumor type-specific PRO (see [Section 11.3](#)).
- Record vital signs (blood pressure, pulse rate, body temperature, and respiratory rate). Measurements will be obtained after 3 minutes in the sitting position. No other measurements or procedures were performed during this 3-minute period.
- Record weight.

At **Visit 17 (Day 259), Visit 19 (Day 399), Visit 20 (Day 483), Visit 21 (Day 567), Visit 22 (Day 651), Visit 23 (Day 735), Visit 24 (Day 819), Visit 25 (Day 903), Visit 26 (Day 987), Visit 27 (Day 1071), and Visit 28/End of Study (Day 1127)**, the following visit procedures will include:

- Perform a CT ( $\pm 14$  days) with contrast. For subjects with IV contrast allergy/intolerance, MRI may be performed. The same modality as the screening imaging assessment should be used throughout the trial.
- Collect a serum sample for CA-125/CA 19-9/CEA for appropriate tumor type (local laboratory).

At **Visit 20 (Day 483)**, the following visit procedures will include:

- Perform a physical examination, which will be based on institution standard of care (see [Section 12.1.3](#)).

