#### **13.3.3. Efficacy Analysis**

##### **13.3.3.1. Relapse-free survival**

Relapse-free survival will be censored on the date of the last evaluable CT scan on trial for subjects who do not have recurrence and who do not die while on trial. Subjects without any post baseline CT scans will have their RFS time censored on the date of randomization. Subjects who withdraw from the trial (including withdrawal of consent and lost to follow-up) will be censored at the last of the last CT scan. For disease recurrence documented by CT between scheduled evaluations, the actual date of the scan will be used. For death or recurrence after no more than

1 missed evaluation, the date of the event will be the date of recurrence or death, whichever occurs first. For death or recurrence after more than 1 missed evaluation, RFS will be censored at the last evaluable disease assessment.

RFS (in months) is calculated as:

- $[(\text{date of recurrence/death} - \text{date of randomization}) + 1]/30.4375$

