## Final Analysis Statistical Analysis Plan (SAP)

1. The patient reported outcomes (PROs) will include the general QLQ-C30, as well as specific PROs for the subject's tumor type (see Protocol Section 11.6). PROs must be completed prior to other study visit procedures.
2. Physical examinations are defined in Protocol Section 12.1.3.
3. A visit window of  $\pm 14$  days is permitted for imaging assessments during the Follow-up Period. For subjects with IV contrast allergy/intolerance, MRI may be performed.
4. Safety laboratories should include CBC with differential: chemistry to include parameters listed in Protocol Section 12.1.6.3; hematology to include parameters listed in Protocol Section 12.1.6.1; coagulation to include parameters listed in Protocol Section 12.1.6.2. Cytokine laboratories IL-2, IFN $\gamma$ , IL-6, IL-10, and TNF $\alpha$ . Serum biomarkers CA- 125 [ovarian], CA19-9 [PDAC] or CEA [CRC]. Details for central laboratory sample collections are provided in the Central Laboratory Manual
5. ctDNA blood testing will occur at a central laboratory. Details for blood collection are provided in the Central Laboratory Manual
6. The PBMCs may be used for immunogenicity and/or biomarker genetic sequencing. Details for central laboratory sample collections are provided in the Central Laboratory Manual.
7. Long-term observation for post dose vaccination adverse events will be recorded if an adverse event began within 30 days of last dose of treatment and continues in the follow-up period.. See Protocol Section 6.7 for instructions regarding signs of toxicity.
8. If new lesions are observed on radiographic imaging, a standard of care biopsy may be performed per iRECIST criteria to confirm disease progression and when the investigator judges that tissue can be safely obtained. If there is sufficient tissue obtained from the biopsy, the pathology lab should perform in situ gene expression and/or IHC for evaluation of tumor infiltrating T cells and the tumor microenvironment.

Final Analysis  
Statistical Analysis Plan (SAP)

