**Table 16: Censoring Rules for RFS, 1-Year RFS and OS**

**Final Analysis  
Statistical Analysis Plan (SAP)**

Situation	Event or censored date	Event or Censored
Censoring Rules for RFS/Primary Analysis		

No subsequent anti-cancer therapy initiated or lost to follow up/withdrawal of consent for follow up:                      Death or recurrence (iCPD)
 
No recurrence or death
	
Date of recurrence (iCPD) or death, whichever occurs first
 
Date of last evaluation CT/MRI visit, without documentation of recurrence of disease (iUPD or absence of progression)
	
Event
 
Censor

Subsequent anti-cancer therapies initiated:                      Death or recurrence (iCPD) after no more than 1 consecutive missed CT/MRI evaluation (ie, <math>\leq 182</math> days (24 weeks + 2 weeks) after start of subsequent anti-cancer therapies
 
No recurrence or death after no more than 1 consecutive missed CT/MRI evaluation (ie, <math>\leq 182</math> days (<math>\leq 24</math> weeks + 2 weeks) after start of subsequent anti-cancer therapy
	
Date of recurrence (iCPD) or death, whichever occurs first, according to the following:                      If death occurs without recurrence, then event is the date of death                      If recurrence occurs prior to death, then the date of last evaluable CT/ MRI visit, without documentation of recurrence of disease (iUPD or absence of progression), that is done before the start of subsequent anti-cancer therapy
 
Date of last evaluable CT/ MRI visit, without documentation of recurrence of disease (iUPD or absence of progression), that is done before the start of subsequent anti-cancer therapy
	
Event
 
Censored

Incomplete or no baseline assessment	Date of start of treatment (censored on Day 1)	Censored
No post baseline CT/MRI scans	Date of start of treatment (censored on Day 1)	Censored
Treatment discontinuation for undocumented progression or for toxicity	Date of last evaluation CT/MRI visit, without documentation of recurrence of disease ( iUPD or absence of progression)	Censored
Censoring Rules for RFS/Secondary Analysis		

**Final Analysis  
Statistical Analysis Plan (SAP)**

Situation	Event or censored date	Event or Censored

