
No subsequent anti-cancer therapy initiated or lost to follow up/withdrawal of consent for follow up:                      Death or recurrence (iCPD)
 
No recurrence or death
	
Date of recurrence (iCPD) or death, whichever occurs first
 
Date of last evaluation CT/MRI visit, without documentation of recurrence of disease (iUPD or absence of progression)
	
Event
 
Censor

Subsequent anti-cancer therapies initiated:                      Death or recurrence (iCPD) after no more than 1 consecutive missed CT/MRI evaluation
 
No recurrence or death after no more than 1 consecutive missed CT/MRI evaluation
	
Date of recurrence (iCPD) or death, whichever occurs first, according to the following:                      If death occurs without recurrence, then event is the date of death                      If recurrence occurs prior to death, then the date of last evaluable CT/ MRI visit, without documentation of recurrence of disease (iUPD or absence of progression)
 
Date of last evaluable CT/ MRI visit, without documentation of recurrence of disease (iUPD or absence of progression)
	
Event
 
Censored

Incomplete or no baseline assessment	Date of start of treatment (censored on Day 1)	
No post baseline CT/MRI scans	Date of start of treatment (censored on Day 1)	Censored
Treatment discontinuation for undocumented progression or for toxicity	Date of last evaluation CT/MRI visit, without documentation of recurrence of disease ( iUPD or absence of progression)	Censored
Censoring Rules for OS		
Death	Date of death	Event
No event prior to data cut-off date	Last known date that the subject was alive.	Censored
No event due to lost to follow-up	Last known date that the subject was alive.	Censored

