### 13.6.2 Analysis of Median RFS

Relapse-free survival (RFS), defined as time from first dose of ELI-002 2P until recurrence/ death. RFS (in months) is calculated as:

$$[(\text{date of recurrence/death} - \text{date of first ELI-002 dose2P dose}) + 1]/30.4375$$

Censoring details are described in Table .

Median RFS will be estimated using the Kaplan-Meier method. Number of subjects with events (recurrence/death) and number of subjects censored and reason of censoring will be presented along with an estimate for median time (days), Q1, and Q3. A Kaplan-Meier plot for time to event will also be provided by cohort. Tables and figures will be created for each of the two censoring rules presented in Table 16 for RFS.

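### SAP Table 16, primary RFS rule: 182 days matches one missed CT/MRI only for last scans on Days 399 to 903, so after a Day 148 or Day 259 scan some deaths following a single missed scan fall outside the limit

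*SAP*

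**What the plan says.** SAP 13.6.1, Table 16, gives a primary and a secondary set of RFS censoring rules. For subjects who start subsequent anti-cancer therapy, the primary rule keeps a death or recurrence as an event if it comes "after no more than 1 consecutive missed" CT/MRI evaluation. It then explains this, as an equivalence, as no more than 182 "days (24 weeks + 2 weeks) after start of subsequent anti-cancer therapies". The paired cell for subjects without an event repeats the limit. Two brackets open and only one closes, so the 182 days could run from the start of the new therapy (as printed) or from the last scan.

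The secondary rule uses the same missed-scan wording with no day limit, and SAP 13.6.2 reports both: "Tables and figures will be created for each of the two censoring rules presented in Table 16 for RFS". Protocol 13.3.3.1 also counts scans, not days: "For death or recurrence after more than 1 missed evaluation, RFS will be censored at the last evaluable disease assessment". Subjects with no post-baseline scan have their own row, "Date of start of treatment (censored on Day 1)", so Day 148 is the earliest scheduled last scan that matters here.

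**The concern.** The rule offers a count of missed scans and a number of days as the same thing. On the trial's own CT schedule they differ for several positions of the last scan, so the words and the number can classify one death differently and the programmer must choose.

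A death that the words keep as an event could be censored months earlier under the number. Early in follow-up that would also remove a failure from 1-year RFS. Kaplan-Meier plots are made by cohort, and cohorts hold 3 to 6 subjects, so one reclassified death is one of very few. Because RFS is shown under both rules, part of any difference between the two results could come from this mismatch and not from the handling of new therapy.

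SAP 14.0 does not list the 182-day limit as a change from the protocol, although the revision history does record new RFS windows and censoring rules for Version 3.0.

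**Working it through.** **Inputs.** First dose is Day 57 (SAP Table 3). Scheduled post-baseline CTs are Day 148 (SAP Table 4), Days 259, 399, 483, 567, 651, 735 and 819 (SAP Table 6), and Days 903, 987, 1071 and 1127 (SAP Table 7). Protocol 10.5 agrees ("Visit 17 (Day 259), Visit 19 (Day 399), Visit 20 (Day 483), Visit 21 (Day 567" and onward), and no CT is due at Day 315. Table 6 footnote 3 gives the window: plus or minus 14 "days is permitted for imaging assessments during the Follow-up Period". Table 4 gives the same window for Day 148.

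**Gaps between scans.** 111, 140, then 84 eight times, then 56 days.

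**The plan's figure.** (24 + 2) × 7 = 182, and 2 × 84 + 14 = 182. It is two 12-week intervals plus the window.

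**Days needed to allow one missed scan**, counted from the last scan: (day of the second following scan − day of last scan) + 14.

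| Last scan | Missed | Next due | Span | +14 | 182 minus this |
|---|---|---|---|---|---|
| Day 148 | 259 | 399 | 251 | 265 | −83 |
| Day 259 | 399 | 483 | 224 | 238 | −56 |
| Days 399 to 903 (7 positions) | – | – | 168 | 182 | 0 |
| Day 987 | 1071 | 1127 | 140 | 154 | +28 |

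**Clock at therapy start.** If therapy begins t days after the last scan, the limit falls on (last scan + t + 182). The shortfall is max(0, 83 − t) for Day 148 and max(0, 56 − t) for Day 259. The documents give no value for t, so a range is assumed:

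| t (days) | 0 | 14 | 28 | 42 | 56 | 69 | 83 |
|---|---|---|---|---|---|---|---|
| Day 148 shortfall | 83 | 69 | 55 | 41 | 27 | 14 | 0 |
| Day 259 shortfall | 56 | 42 | 28 | 14 | 0 | 0 | 0 |

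The one-missed-scan interval, window included, runs from Day 273 to 413 (140 days) after a Day 148 scan and from Day 413 to 497 (84 days) after a Day 259 scan. At t = 0 the part outside the limit is 83/140 = 59% and 56/84 = 67%. At t = 28 it is 55/140 = 39% and 28/84 = 33%. These are shares of calendar time, not of deaths.

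**Examples that fail under either reading of the brackets** (nominal days, t = 1):

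- Last scan Day 148, therapy Day 149, Day 259 scan missed, death on Days 332 to 398: 183 to 249 days from therapy and 184 to 250 from the scan.
- Last scan Day 259, therapy Day 260, Day 399 scan missed, death on Days 443 to 482: 183 to 222 days from therapy and 184 to 223 from the scan.

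**Effect on RFS for such a subject**, using the SAP 13.6.2 formula, months = (day − 57 + 1)/30.4375, and assuming a death past the limit is censored at the last scan:

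- Day 148 case: an event at 276/30.4375 = 9.1 to 342/30.4375 = 11.2 months becomes censoring at 92/30.4375 = 3.0 months. One year from first dose is 57 + 365 = Day 422, so these deaths would drop out as failures in 1-year RFS.
- Day 259 case: an event at 387/30.4375 = 12.7 to 426/30.4375 = 14.0 months becomes censoring at 203/30.4375 = 6.7 months.

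**The opposite error.** Counted from therapy start, the limit can also let in a death after two missed scans: last scan Day 399, therapy Day 460, Days 483 and 567 missed, death Day 600. That is 140 days from therapy but 201 from the scan.

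**The case against.** The arithmetic is hard to dispute. The objections concern reach, and most of them stand.

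- **The shortfalls are maxima.** With the clock at therapy start, 83 and 56 days shrink by one day for each day of lag and reach zero at lags of 83 and 56 days. A reader might infer that every death after one missed scan is excluded. That is not so: only the later part of the interval is affected, and only when therapy starts soon after the scan.
- **The Day 148 example assumes nominal visit days.** New anti-cancer treatment ends trial treatment, after which the subject has the Visit 15 procedures and enters follow-up (Protocol 6.7.2 and 7.3). The documents do not say whether later visits keep their nominal days. If they were re-timed from end of treatment, Visit 17 would fall at 259 − 217 = 42 days and Visit 19 at 399 − 217 = 182 days, and the mismatch would largely vanish for that case. The Day 259 case is unaffected.
- **Frequency is unknown.** A reader might take the protocol's "an expected median relapse-free survival (RFS) of only 5 months" for ctDNA-positive resected pancreatic subjects as evidence that the misfit sits where relapse is expected. It does not show that. A relapse confirmed before new therapy is already an event, and one found afterwards is dated back to the last recurrence-free scan before therapy. The date shift therefore concerns mainly deaths without prior confirmed recurrence, and a relapse median says nothing about how often those follow exactly one missed scan.
- **Late events may not lack a rule.** The paired censoring cell can be read to cover events past the limit. It does not say so plainly.
- **There is a safeguard.** The secondary rule has no day limit, both versions are reported, reasons for censoring are tabulated, and efficacy data are listed by patient.

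None of this restores the equivalence that the cell asserts.

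**Conclusion.** The point holds in a limited form. The number in the primary rule does not equal the missed-scan count it is said to express, except for last scans on Days 399 to 903 counted from that scan. It is too short by at most 83 days after a Day 148 scan and at most 56 after a Day 259 scan, in each case less any lag to therapy. It is 28 days too long after Day 987, where data are likely sparse because long-term follow-up ended early (SAP 14.0).

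The effect is confined to exploratory RFS and 1-year RFS in probably few of the approximately 18 planned subjects. No shift in median RFS is claimed, nor any frequency. The per-subject figures rest on nominal visit days and on late deaths being censored at the last scan before therapy. Confidence is high in the arithmetic and low in any statement about impact. The cell is still worth correcting, because it is a decision rule that can turn a death from an event into a censored time.

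**What to change.** In both primary-rule cells of SAP Table 16, delete the 182-day equivalence and count consecutive missed scheduled CT/MRI evaluations, as Protocol 13.3.3.1 and the secondary rule do. Add one statement: death or recurrence after two or more consecutive missed scans is censored at the last evaluable CT/MRI without recurrence done before the start of subsequent anti-cancer therapy. This keeps the primary rule's pre-therapy condition, and with it the difference from the secondary rule. Leave the Day 1 censoring row for subjects with no post-baseline scan as it is.

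A list of day limits by last scan is a weaker repair, because unscheduled imaging is allowed at any time and would fall between the listed days.

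Alternatively, if a 182-day limit after new therapy is what is meant, state it as that, remove the missed-scan wording, close the bracket, say how later events are handled, and list it in SAP 14.0 as a change from the protocol.

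Cost: two table cells and one added statement (or one entry in SAP 14.0). No new data are needed.

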### **6.1.2. Criteria for Booster and Additional Booster Vaccines**

Accumulating clinical evidence indicates some subjects treated with an immunotherapy, such as ELI-002, may be assessed as having disease progression by conventional response criteria before demonstrating clinical objective responses and/or stable disease [[Wolchok et al, 2009](#)]. This pseudoprogression has been observed in the ELI-002-001 trial. Two hypotheses have been suggested to explain this phenomenon. The first is that enhanced inflammation within the lesions could lead to an increase in the lesion size which would appear as enlarged index lesions and therefore as newly visible small non-index lesions. Over time, both the malignant and inflammatory portions of the lesion(s) may then decrease leading to overt signs of clinical improvement. The second hypothesis is that, in some subjects, the speed of the lesion growth may initially outpace the anti-tumor immune activity of the therapy. With sufficient time, the anti-tumor activity will dominate and become clinically apparent. Therefore, subjects participating on ELI-002-001 will be allowed to continue ELI-002 treatment, as specified in this protocol, after initial investigator assessed progression (iUPD via iRECIST) if the subject is deriving clinical benefit and tolerating the study treatment well in the judgement of the investigator. Subjects must discontinue treatment upon confirmed disease progression.

All subjects free of confirmed radiographic progression will receive booster doses unless they have unresolved toxicity. For subjects which have encountered signs of toxicity, the investigator must consult with the sponsor's medical monitor who must agree with resuming the subsequent booster vaccinations (see [Section 6.7.1](#)).

Subjects who remain in the trial until the end of the required Follow-up Period may be eligible to enroll in a separate extension protocol to continue to receive further lymph node antigen exposure to maintain effective levels of antigen-specific T-cells.

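### SAP Table 16 dates some relapses at a scan that showed none, and its no-scan and toxicity rows censor subjects whose death or relapse is observed, with no rule on which row prevails

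*SAP*

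**What the plan says.** SAP 13.6.2 defines RFS as "defined as time from first dose of ELI-002 2P until recurrence/ death" and refers to Table 16 for censoring. Table 16 holds a primary and a secondary rule set, and both are reported: "Tables and figures will be created for each of the two censoring rules presented in Table 16 for RFS".

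- **First row, both sets.** With no new anti-cancer therapy, death or confirmed recurrence (iCPD) is an event on its own date.
- **New-therapy row, primary set.** The date cell begins with the date of iCPD "or death, whichever occurs first, according to the following". Death without recurrence is dated at death. For the other case it says: "If recurrence occurs prior to death, then the date of last evaluable CT/ MRI visit, without documentation of recurrence of disease", with the scan being one "that is done before the start of subsequent anti-cancer therapy". As the table reads in the available text, the status column has two entries, Event and Censored, for two paragraphs. This line belongs to the Event paragraph.
- **New-therapy row, secondary set.** The wording is the same without the before-therapy limit.
- **"No post baseline CT/MRI scans", both sets.** Censored on Day 1.
- **"Treatment discontinuation for undocumented progression or for toxicity", both sets.** Censored at the last scan without documented recurrence.

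Protocol 13.3.3.1 dates an event at recurrence or death after no more than one missed evaluation. It also censors subjects without post-baseline scans at the start, and it has no toxicity censoring rule. SAP section 14.0 does not list the toxicity row as a change from the protocol.

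**The concern.** There are three faults.

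**(a) Event date.** In the primary set, a relapse counted as an event is placed on a scan that did not confirm it. If therapy began after an unconfirmed progression (iUPD), that is the iUPD scan. If therapy began while the last scan was clear, it is a scan with no relapse at all. Either way it conflicts with the cell's own opening, with SAP 13.6.2 and with the protocol's event-date sentence. In the secondary set the same words ordinarily lead to the iUPD scan, because iCPD follows an iUPD. The fault there is mainly inconsistency with the first row, which uses the iCPD date.

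**(b) No-scan row.** A subject who dies before any post-baseline scan meets the first row (event) and this row (censored on Day 1).

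**(c) Toxicity row.** Protocol 6.7.2 keeps subjects who stop treatment in follow-up, and SAP Table 7 note 6 follows everyone for disease status. Later relapses and deaths are therefore observed, yet this row would censor them.

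SAP 12.2, 13.6.1 and 13.6.2 do not say which row prevails. SAP 13.6.2 asks for counts of events, counts censored and reasons for censoring. Those counts are not uniquely defined, in a trial planned for about 18 subjects whose efficacy summaries are meant (SAP 13.1) to inform later designs.

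**Working it through.** **Inputs.** First dose is Day 57 (Protocol Table 12). CT visits fall on Days 148, 259, 399 and 483 (Protocol Tables 13 and 15), which is 91, 202, 342 and 426 days after first dose. RFS in months = (day − 57 + 1)/30.4375 (SAP 13.6.2).

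**The plan's own figure.** The one-missed-scan window is (24 + 2) × 7 = 182 days, as Table 16 states.

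**(a) One subject: clear on Day 259, unscheduled iUPD on Day 350, iCPD on Day 399**

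| Situation | Date used | RFS |
|---|---|---|
| No new therapy | Day 399 | 343/30.4375 = 11.27 months |
| New therapy Day 300, primary | Day 259 | 203/30.4375 = 6.67 months |
| New therapy Day 300, secondary | Day 350 | 294/30.4375 = 9.66 months |

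iCPD comes 399 − 300 = 99 days after the new therapy, inside the 182-day limit.

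For the group effect, assume exponential RFS, S(t) = exp(−ln 2 × t/median). The medians come from the protocol's background cohorts: 5 months (4.6.4) and 10.4 months (4.1.1). Let a share p of relapsers start therapy between a clear scan and the relapse scan. Those found at 426 days are then moved back to 342 days, so 1-year RFS = (1 − p)S(342) + pS(426).

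- 5 months: S(342) = 0.211, S(426) = 0.144. For p = 0.1 to 0.5, 1-year RFS is 20.4% to 17.7% instead of 21.1%.
- 10.4 months: S(342) = 0.473, S(426) = 0.393. It is 46.5% to 43.3% instead of 47.3%.

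The shift is smaller than one subject in 18 (1/18 = 5.6 points).

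**(b) Death on Day 140 with no scan.** First row: event at 84/30.4375 = 2.76 months. No-scan row: censored at 1/30.4375 = 0.03 months. With 1, 2 or 3 such deaths among 18, RFS just before the first scan should be 17/18 = 94.4%, 16/18 = 88.9% or 15/18 = 83.3%. Day-1 censoring gives 100%. The exposed window is 148 − 57 = 91 days by the schedule, or 35 days if the CT mentioned in the protocol synopsis is done.

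**(c) Toxicity stop on Day 92, clear to Day 399, iUPD Day 483, iCPD Day 511.** First row: event at 455/30.4375 = 14.95 months. Toxicity row: censored at the Day 483 scan, 427/30.4375 = 14.03 months.

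For the group effect, let a random share q stop, with those who relapse censored at their last clear scan. The Kaplan-Meier estimate is the product over scans j at 91, 202 and 342 days of 1 − (1 − q)(S[j−1] − S[j]) / ((1 − q)S[j−1] + qS[j]).

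| q | 5-month median (true 21.1%) | 10.4-month median (true 47.3%) |
|---|---|---|
| 0.1 | 0.684 × 0.628 × 0.555 = 23.8% | 50.6% |
| 0.2 | 27.1% | 54.1% |
| 0.3 | 31.0% | 58.1% |

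A simulation of 400,000 subjects at the 5-month median gave 23.8%, 27.0% and 30.9%. With stop times spread over 0 to 160 days and applied only before relapse, it gave 23.4%, 26.2% and 29.5%. If censoring is instead at the iUPD scan and iCPD comes 28 days later, relapses found at day 342 are confirmed at day 370, past one year. The true value is then about 40%, and the row gives about 43% to 50%.

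**Row choice alone.** Take an assumed cohort of six: a death on Day 120 with no scan; a relapse on Day 399 after therapy on Day 300 with a clear Day 259 scan; a toxicity stop clear to Day 399 with relapse confirmed on Day 483; a toxicity stop clear on Day 259 with death on Day 300; and two event-free subjects censored on Days 651 and 735. Observed dates give 4 events and a median of 11.27 months. Table 16 with its event rows prevailing gives 4 events and a median of 8.02. With its censoring rows prevailing it gives 1 event and the median is not reached.

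**The case against.** The relapse line in (a) nearly repeats the next paragraph, which is labelled Censored, so it may be a censoring date under the wrong status. That is possible, but the table then has to say so, because event or censored is the basic output of the derivation. The cell's opening is also qualified by what follows it, and SAP 13.6.2 defers to Table 16. Even so, a line that dates an event at a scan without recurrence is not a workable reading of a definition that runs to recurrence or death. Where therapy follows an iUPD, the resulting date is a defensible convention; the fault there is only that other subjects are dated by iCPD.

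On (b), the protocol paragraph opens by limiting censoring to subjects who neither relapse nor die, and its no-scan sentence can be read within that limit. Table 16 carries no such limit. Unscheduled CT is allowed and entry requires ECOG 0 or 1, so early deaths without a scan may be few.

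On (c), the documents give no toxicity-stopping rate. Protocol 4.6.3 names injection site reaction as the only attributed adverse event, and toxicity may first lead to a dose hold. The percentages illustrate size and are not predictions.

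RFS is exploratory, no dose decision depends on it, and the reported reasons for censoring would expose some of the problem. This limits the consequence but does not make the derivation unique.

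**Conclusion.** The concern holds. Followed as written, Table 16 gives some relapses the wrong date and allows observed deaths and relapses to be dropped. This is an error in the rules, not just missing detail. Part (a) applies in full to the primary analysis and as an inconsistency to the secondary; (b) and (c) apply to both.

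Backdating moves 1-year RFS by 0.7 to 4.0 points under the assumed shares. Random toxicity stopping at 10% to 30% raises it by 2.7 to 9.9 points at the 5-month median and by 3.3 to 10.8 at the 10.4-month median. Backdating shortens RFS, while (b) and (c) lengthen it. The therapy shares, early deaths and stopping rates are assumptions, the medians are from background cohorts, and the exponential form is a simplification. That the rows overlap without stated precedence depends on none of these. The point should be fixed before the analysis is run.

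**What to change.** For both rule sets in Table 16:

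1. State one recurrence-date convention, either iCPD or the first iUPD if later confirmed, for every subject counted as an event. Never date an event at a scan without recurrence. If the intent is to censor at new therapy, set the status of that line to Censored.
2. Limit Day-1 censoring to subjects alive with no post-baseline scan. Count death as an event, subject to one missed-scan rule.
3. Remove the toxicity and undocumented-progression row, or limit it to subjects with no later observed recurrence or death.
4. State which row prevails when a subject meets more than one.

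A sensitivity analysis counting iUPD followed by new anti-cancer therapy as an event is optional.

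The cost is SAP wording and the reprogramming of one derivation, with no new data. Reported RFS may move in either direction.
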